9.4.2 Primary Endpoint

The primary endpoint is the overall incidence of RSV LRTI hospitalization through the RSV season in healthy term and preterm infants in all 3 countries combined. The determination of RSV LRTI hospitalization is based on the criteria described in Section 8.1.2.2.

The efficacy of nirsevimab in preventing RSV LRTI hospitalization compared to no intervention will be estimated accounting for the follow-up time post-dosing/randomization up to the data cut-off date for the Primary Analysis as follows:

 $(1-(CN/NN)/(CC/NC)) \times 100\%$

where:

- CN and CC are the numbers of RSV LRTI hospitalization through the RSV season in the nirsevimab and the control (ie, no intervention) groups, respectively.
- NN and NC are the total person-time contributed by participants randomized in the nirsevimab and the control groups, respectively.

The 95% CI for the efficacy will be calculated by an exact method assuming a binomial distribution of the number of RSV LRTI hospitalizations in the nirsevimab group conditional on the total number in both groups accounting for the follow-up time post-dosing/randomization.

The superior efficacy of nirsevimab in preventing RSV LRTI hospitalization will be concluded if the lower bound of the efficacy is > 0%. The primary efficacy analysis of the primary endpoint will be performed on all randomized participants.

If a participant experiences multiple occurrences of the same primary endpoint, only the first episode will be considered. The following rules will be applied in the calculation of the total person-time for the follow-up time:

- The start date for the follow-up will be the date of randomization for participants who are randomized to no intervention and the date of dosing for participants who are randomized to nirsevimab.
- For the participants who do not have the primary endpoint at the time of the Primary Analysis, the end date for the efficacy follow-up will be the end of the RSV season, or the last available date with confirmation of no RSV LRTI hospitalization for the Primary Analysis whichever is earlier. The efficacy follow-up will be censored at the end date.
- For the participants who have the primary endpoint at the time of the Primary Analysis, the end date for the efficacy follow-up will be the date of hospital admission.

The above-described analysis on the primary endpoint will also be conducted on the PPAS.

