2.4. Primary Efficacy Variable

The primary efficacy variable is the overall incidence of RSV LRTI hospitalization through the RSV season.

“Hospitalization” is defined as the decision to admit to in-patient care by a physician.

“RSV season” is the period of increased RSV infection. For the purpose of efficacy analyses, the start and end dates of the RSV season will be defined on a country-by-country basis and will be based on country-specific epidemiological surveillance. Methodology to define the season will be agreed upon with the National Core Investigators (NCI) and described in detail. Methodology will depend on RSV circulation, hence, an a priori definition is not possible due to the impact of COVID and related public health measures.

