6.6.1. Primary Efficacy Analysis

The primary efficacy variable is defined as the overall incidence of RSV LRTI hospitalization through the RSV season in healthy term and preterm infants in all 3 countries combined, measured by $1 - \text{incidence rate ratio}$.

The null hypothesis of $(1 - (CN / NN) / (CC / NC)) \times 100\% \leq 0\%$ will be tested against the alternative hypothesis of $(1 - (CN / NN) / (CC / NC)) \times 100\% > 0\%$ at the $\alpha=0.05$ significance level.

where:

- CN and CC are the numbers of RSV LRTI hospitalization through the RSV season in the nirsevimab and the no intervention groups, respectively.
- NN and NC are the total person-time contributed by participants randomized in the nirsevimab and the no intervention groups, respectively.

If a participant experiences multiple occurrences of the same primary endpoint, only the first episode will be considered.

The following rules will be applied in the calculation of the total person-time for the follow-up time:

- The start date for the follow-up will be the date of randomization for participants who are randomized to no intervention, the date of treatment dosing for participants who are randomized to nirsevimab and treated, and the date of randomization for participants who are randomized to nirsevimab but not treated.
- For the participants who have the primary endpoint at the cut-off date for the Primary Analysis, the end date for the efficacy follow-up will be the date of hospital admission if the cut-off date is before the end of RSV season; otherwise the participants will be censored at the end of RSV season.
- For the participants who do not have the primary endpoint at the cut-off date for the Primary Analysis (see section 6.7.8), the efficacy follow-up will be censored at the end date defined in the following:
 - for the participants who continue in the study and had contact for safety events, the end date for the efficacy follow-up will be the end of RSV season, the last available date with confirmation of no RSV LRTI hospitalization or the cut-off date whichever is earlier.
 - for the participants who discontinued from the study before the end of RSV season and had contact for safety events, see Table 2 in section 3.1.4.

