 - for the participants who had no contact for safety events at all throughout the efficacy follow-up period, the end date for the efficacy follow-up will be date of randomization for participants who are randomized to no intervention, the date of treatment dosing for participants who are randomized to nirsevimab and treated, and the date of randomization for participants who are randomized to nirsevimab but not treated.

The total person-time for the follow-up time of each participant will be calculated as:

Person-months = (the end date - the start date + 1)/30.4375.

NN (days), the total person-time contributed by participants randomized in the nirsevimab, will be the sum of person-months for all the participants in the nirsevimab group. And NC (days), the total person-time contributed by participants randomized in the no intervention group, will be the sum of person-months for all the participants in the no intervention group.

The 2-sided 95% CI for the efficacy will be calculated by an exact method assuming a binomial distribution of the number of RSV LRTI hospitalizations in the nirsevimab group conditional on the total number in both groups (described by Breslow and Day⁷) accounting for the follow-up time post-dosing/randomization.

The superior efficacy of nirsevimab in preventing RSV LRTI hospitalization is concluded if the lower bound of 2-sided 95% CI of the efficacy is $> 0\%$. P-value will also be provided. The primary efficacy analysis of the primary endpoint will be performed with the All Randomized Set.

RSV season is the period of increased RSV infection. For the purpose of efficacy analyses, the start of the RSV season will be defined on a country-by-country basis and will be based on country-specific epidemiological surveillance and the cut-off date (28Feb2023, except for site parent contact and medical call center contact, for which the date of database lock for Primary Analysis will be used) will be used as end dates.

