6.6.3.2. Survival Analyses

A hazard ratio and the corresponding 2-sided 95% CI will be obtained from the Cox proportional hazard model with country (ie, France, Germany and United Kingdom) and age group at randomization (ie, age \leq 3.0 months, age $>$ 3.0 to \leq 6.0 months, age $>$ 6.0 months) as the covariates. The corresponding efficacy estimate is defined as $(1 \text{ minus hazard ratio}) \times 100\%$. A Kaplan-Meier curve for time to first RSV LRTI hospitalization will be generated based on the observed events and will include the p-value from a log-rank test stratified by country and age group at randomization. The algorithm for time-to-event calculation is the same as that for follow-up time as Section 6.6.1.

A log log plot to check Proportional Hazard assumption in the Cox proportional hazard model above will be provided.

Above analyses will be performed in the All Randomized Set.

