6.6.7.8. Follow-up

Number and percentage of participants will be provided for:

- Monthly responses in eDiary according to the analysis window in Section 5.1.4.

In addition, at the time of First Year Analysis, follow-up time in months will be described for all participants (based on the primary endpoint RSV LRTI Hospitalizations), participants with RSV LRTI Hospitalizations, participants with Very Severe RSV LRTI, participants with Hospitalizations for all-cause LRTI at the following timeframes (see Section 6.1 for details on the descriptive statistics):

- Through the RSV Season (overall and in each country)
- Through Day 151 post-dosing/randomization (overall and in each country)
- Through Day 181 post-dosing/randomization (overall and in each country)
- From 181 days post-dosing/randomization to 366 days post-dosing/randomization in participants with no event before Day 181 (overall and in each country, excluding participants with very severe RSV LRTI)

Follow-up time in months will also be summarized at the time of Second Year analysis:

- From 366 days post-dosing/randomization to 731 days post-dosing/randomization in UK reconsented participants. However, this will not be summarized for subgroup of participants with Very Severe RSV LRTI.
- From 366 days post-dosing/randomization to 511 days post-dosing/randomization in UK reconsented participants. However, this will not be summarized for subgroup of participants with Very Severe RSV LRTI.
- From 512 days post-dosing/randomization to 731 days post-dosing/randomization in UK reconsented participants. However, this will not be summarized for subgroup of participants with Very Severe RSV LRTI.
- Through Day 511 post-dosing/randomization in UK reconsented participants. However, this will not be summarized for subgroup of participants with Very Severe RSV LRTI.
- Through Day 731 post-dosing/randomization in UK reconsented participants. However, this will not be summarized for subgroup of participants with Very Severe RSV LRTI.
- Through Day 366 post-dosing/randomization in UK reconsented participants (recurrent wheeze event)
- From Day 366 post-dosing/randomization to Day 731 post-dosing/randomization in UK reconsented participants (recurrent wheeze event)
- Through Day 731 post-dosing/randomization in UK reconsented participants (recurrent wheeze event)

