6.6.7.10. Rerun of Primary Analysis at the Time of First Year Analysis

The Primary Analysis will be re-run at the time of the First Year Analysis considering the same cut-off date and the same rules as the Primary Analysis.

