6.6.9.2.1. Algorithm for Follow-up Time

The start date for the follow-up will be the date of randomization for participants who are randomized to no intervention, the date of treatment dosing for participants who are randomized to nirsevimab and treated, and the date of randomization for participants who are randomized to nirsevimab but not treated.

For the participants who have the event of interest in the corresponding timeframe for the Second Year Analysis, the end date of the follow-up time will be the date of hospital admission; otherwise the participants will be censored as defined in the following:

- **From 366 Days Post-Dosing/Randomization to 511 Days Post-Dosing/Randomization**

The analysis will be performed only in participants without the studied event before Day 366.

For UK reconsented participants who completed the study, the end date of the follow-up time will be Day 511 or last available date with confirmation of no RSV/all-cause LRTI hospitalizations, whichever is earlier.

For UK reconsented participants who had contact for safety events after reconsented and discontinued from the study before Day 511, the end date of the follow-up time will be the last available date with confirmation of no RSV/all-cause LRTI hospitalizations.

For UK reconsented participants who had no contact for safety events at all after reconsenting, the end date of the follow-up time will be the reconsent date.

Notes:

- If the event of interest occurs after Day 511, it will not be considered and then the end date will be Day 511.
- If a participant receives Beyfortus as part of a routine immunization, any event occurring after Beyfortus immunization but between Day 366 and Day 511 will not be considered and the end date will be the date of injection of Beyfortus.

- **From 512 Days Post-Dosing/Randomization to 731 Days Post-Dosing/Randomization**

The analysis will be performed only in participants without the studied event before Day 512.

For UK reconsented participants who completed the study, the end date of the follow-up time will be Day 731 or last available date with confirmation of no RSV/all-cause LRTI hospitalizations, whichever is earlier.

For UK reconsented participants who had contact for safety events after reconsented and discontinued from the study, the end date of the follow-up time will be the last available date with confirmation of no RSV/all-cause LRTI hospitalizations.

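### SAP 6.6.1 makes the end of a case's follow-up depend on the cut-off date, not the admission date, so as written no case's time ends at admission

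*SAP*

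**What the plan says.** SAP 6.6.1 (Primary Efficacy Analysis) gives the following end of follow-up for a participant with the primary endpoint: "date of hospital admission if the cut-off date is before the end of RSV season; otherwise the participants will be censored at the end" (that is, season end). Later in the section the season start is left to country surveillance, but the season end is fixed. It is the cut-off date of 28 February 2023, with an exception for site and call-centre contacts, "for which the date of database lock for Primary Analysis will be used) will be used as end dates".

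Three other places bear on this:

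- Protocol 9.4.2, for participants with the endpoint: "the end date for the efficacy follow-up will be the date of hospital admission". There is no condition.
- SAP 6.6.9.2.1, for the post-hoc UK analyses: "the end date of the follow-up time will be the date of hospital admission; otherwise the participants will be censored". Only participants without the event are censored.
- SAP 2.4: "the start and end dates of the RSV season will be defined on a country-by-country basis". This differs from the fixed end date in 6.6.1.

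The 6.6.1 rule is reused widely. SAP 6.6.3.2 states: "The algorithm for time-to-event calculation is the same as that for follow-up time as Section 6.6.1". The Poisson offset (6.6.2.1) and the very severe and by-country analyses refer back to it as well. The re-run in 6.6.7.10 is done "considering the same cut-off date and the same rules as the Primary Analysis". Section 7, which lists changes from the protocol-planned analyses, does not mention the rule.

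**The concern.** The condition compares two study-level dates and never looks at when the participant was admitted. With season end set equal to the cut-off, it asks whether a date is earlier than itself. An infant admitted in November and one admitted in February would both have time running to 28 February.

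The numerators CN and CC are defined separately, so cases would still be counted in the primary analysis. The error is in person-time and, above all, in event times. Kaplan-Meier curves would place each event at season end, so their shape would reflect enrolment dates rather than the timing of disease. The log-log plots meant to check proportional hazards would have the same fault. In addition, the else branch says that participants who have the endpoint are censored. Read strictly, that removes them as events from the survival analyses. A programmer following the SAP and one following the protocol would build different datasets.

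**Working it through.** **1. The condition.** Cut-off = 28 Feb 2023 and season end = cut-off (SAP 6.6.1). The test 28 Feb 2023 < 28 Feb 2023 is false for everyone. The database-lock exception qualifies the cut-off itself; if the lock date is read as the cut-off, it is later than 28 February and the test is still false. Under the country-specific ends of SAP 2.4, the test is false in every country whose season ended on or before the cut-off, and it still ignores the admission date.

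**2. Design inputs (Protocol 9.2).** 14 430 per arm; 60% efficacy; control incidence 1.1%, or 0.86% as the lowest reported. The plan's event figure reproduces: 9620/2 = 4810 per arm and country, and 4810 × (0.011 + 0.0044) = 74.07, against the stated 74. The sample size does not depend on the rule.

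**3. Effect on the primary estimate by hand.** Efficacy = 1 − (CN/NN)/(CC/NC). At 0.86%: CC = 14 430 × 0.0086 ≈ 124 and CN = 0.4 × 124.1 ≈ 50. Assume a mean follow-up of 3 months, half of a case's time falling after admission (neither is in the documents).

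- Rule as written: NN = NC = 14 430 × 3 = 43 290. Efficacy = 1 − 50/124 = 59.68% (exact 95% CI 43.58 to 71.56).
- Admission date: NN = 43 290 − 50 × 1.5 = 43 215; NC = 43 290 − 124 × 1.5 = 43 104. Efficacy = 1 − (50/43 215)/(124/43 104) = 59.78% (43.72 to 71.64).

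Letting 25% to 100% of case time fall after admission, at either control rate, the difference is 0.05 to 0.27 points, always towards lower efficacy under the rule as written.

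**4. Simulation of the time-based outputs.** 300 trials in each of six scenarios, 14 430 per arm, control risk 1.1% per 151 days, 60% efficacy, no dropout, cut-off = season end = day 181. Entry was uniform over 181 days, uniform over 90 days, or front-loaded (beta 1.5, 3 over 181 days). The hazard was flat or peaked at calendar day 85 (SD 28). Events were counted under both rules; only the end of case time differs. The base case is uniform entry over 181 days with flat hazard (39 v 95 events).

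| Output | Base: admission | Base: as written | Six scenarios |
|---|---|---|---|
| Exact efficacy | 59.07% | 58.96% | mean fall 0.10-0.18 points (largest single trial 0.23) |
| Cox efficacy | 59.06% | 58.93% | mean fall 0.11-0.20 points (largest single-trial difference 1.4-3.8 by scenario) |
| Log-rank z | −4.90 | −4.88 | change 0.03 or less |
| Control KM, day 90 | 0.65% | 0.25% | 0.65-0.99% v 0.00-0.25% |
| Control KM, day 150 | 1.09% | 1.22% | 0.90-1.16% v 0.96-1.32% |
| Control KM, day 179 | 1.29% | 4.26% | 0.9-1.3% v 4.0-5.7% |
| Excess follow-up per case | – | 60.1 days (median 53.1) | mean 60-90 days |

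At least 99.7% of trials were significant under both rules.

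**5. A second simulation** (20 runs, uniform entry 1 September to 28 February, constant hazard, about 49 v 124 cases) shows the same pattern. Admission date against rule as written: efficacy 60.6% v 60.5%; median case time 53 v 128 days; control Kaplan-Meier incidence 0.85% v 0.31% at day 90 and 1.6% v 3.9% at day 175.

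**The case against.** The strongest reply is that this is a wording slip with a recoverable intent. Censoring at season end makes sense for admissions after season end. SAP Table 2 disregards hospitalizations after the cut-off or season end for those who leave the study early, and the Day 151 and Day 181 rules treat later events the same way. SAP 6.6.2.1 speaks of follow-up time of the first event. The code may therefore already use admission dates. That is plausible, but the SAP does not say so, and a rule inherited by reference should be right at its source.

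The Kaplan-Meier figures also rest on one reading, in which the event is counted but placed at season end. That is fair, but a strict reading of censoring is worse: the survival analyses would have no events.

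Several limits stand:

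- The inferential effect is negligible, and the survival analyses are supplementary.
- Day 179 is the sparse tail. With uniform entry about 14 430/181 ≈ 80 controls enter per day, so only some 160 to 240 are still at risk there. The day-150 ranges overlap; day 90 is the informative comparison.
- SAP 6.6.9.2.1 governs different analyses, so it shows inconsistent drafting rather than a competing rule for the same endpoint.
- SAP 6.6.7.8 does not cite 6.6.1 for its end dates; that it inherits the rule for "follow-up time in months will be described for all participants (based on the primary endpoint RSV LRTI Hospitalizations), participants with RSV LRTI Hospitalizations" is an inference.

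**Conclusion.** The concern holds. As written, the admission-date branch cannot be reached, the rule departs from Protocol 9.4.2, and the departure is not declared in SAP section 7. The confirmatory conclusion is not at risk: cases are about 1% of participants, the shift is a fraction of a percentage point, and it runs slightly against nirsevimab. Mean Cox and log-rank results barely move because both arms shift alike. The damage is to Kaplan-Meier curves, log-log plots and the reported through-season follow-up of cases. The rule should be corrected, but this is not a threat to the primary result.

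The logic needs no assumption beyond the season end stated in 6.6.1. The sizes rest on assumed enrolment, season shape and no dropout, none of which the documents give, and on events being counted at season end.

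**What to change.** Replace the bullet for participants with the endpoint by wording such as:

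> If a participant's first RSV LRTI admission falls on or before the earliest of season end, the Primary Analysis cut-off and (where applicable) the start of Beyfortus, the event is counted and follow-up stops on the admission date. If the first admission falls later, the participant is not a case and is censored under the non-case rules and Table 2.

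The Beyfortus clause keeps the bullet consistent with Table 2. Also reconcile the season end in SAP 2.4 with that in 6.6.1.

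Check the code for every analysis that uses the rule: 6.6.2.1, 6.6.2.2 (through NN and NC), 6.6.3.1, 6.6.3.2, 6.6.4.1, 6.6.4.2, 6.6.4.3.1, 6.6.5.1, 6.6.5.2, 6.6.6.1, 6.6.6.2, 6.6.7.7, 6.6.7.10, 6.6.8.1 and 6.6.8.2, and the through-season parts of 6.6.7.3, 6.6.7.8 and 6.6.9.1. If outputs exist, record which rule was coded and list any departure from the protocol in section 7.

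Cost: one sentence in the SAP, a programming check and, if outputs exist, a short note. No new data.

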7.3 Lost to Follow-up

A participant will be considered lost to follow-up if her or his parents or LARs cannot be contacted by the site or designee.

The following actions must be taken if the parents or LARs of the participants do not follow-up on the monthly electronic contact (until 6 months after dosing/randomization) or cannot be contacted by phone at the end of the study as planned in the SoA:

- For the monthly electronic contact: the electronic platform will send one reminder for 3 consecutive days. If there is no answer after the e-reminders, the site and/or designee will call the parents or LARs of the participant as soon as possible, discuss the importance of answering the follow-up questions with them, and ascertain whether or not they wish their infant to continue participating in the study.
 - It is to be noted that if both the electronic and phone reminders fail, the next monthly electronic contact (up until 6 months post-dosing/randomization) will take place. The participant will not be deemed lost to follow-up before the 12-months follow-up phone contact for France, Germany, and UK non-reconsented participants or the 24-months follow-up phone contact for UK reconsented participants takes place.
- For the 12 months follow-up phone contact for France, Germany, and UK non-reconsented participants or the 24 months follow-up phone contact for UK reconsented participants, and before a participant is deemed lost to follow-up, the investigator or designee must make every effort to regain contact with the parents or LARs of the participants (where possible, 3 telephone calls and, if necessary, a certified letter to the participant's last known mailing address or local equivalent methods). These contact attempts should be documented in the participant's medical record.
 - Should the parents or LARs continue to be unreachable, the participant will be considered lost to follow-up.

Discontinuation of specific sites or of the study as a whole are handled as part of Appendix 10.1.

8 Study Assessments and Procedures

- Study procedures and their timing are summarized in the SoA. Protocol waivers or exemptions are not allowed.
- Adherence to the study design requirements, including those specified in the SoA, is essential and required for study conduct.

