8.1 Efficacy Assessments

Planned time points for all efficacy assessments are provided in the SoA.

Efficacy data for the first year of study and descriptive data for the second year of the study are collected through the participant's medical records and reported in the eCRF. Hospitalizations will be reported by parents/LARs of participants through an eDiary for the first year of the study. From D01 to D366, each time a health event will be captured on the eDiary, a medical call center will contact parents/LARs to collect and report the health event's information in the eCRF. The Investigator or delegated site staff will review information reported in the eCRF and interview the participants' parents/LARs if any additional information needs to be collected. Parents/LARs who don't have access to the eDiary will be requested to contact directly the investigation site to report any health event.

From D366 to D731, UK reconsented participants' parents/LARs will record in the memory aid any hospitalization that occurred. During the 18-month and 24 month phone calls, the Investigator or delegated site staff will interview parents/LARs to collect information reported in the memory aid and report only LRTI hospitalization's information in the eCRF.

During the 12- and 24-month follow-up calls, the site investigator or staff designee will ask to parents/LARs of UK reconsented participants if the participants had experienced any medically attended cough, chest or breathing problems throughout the study period. After the 12-month follow-up phone call (when possible) and the 24-month follow-up phone call, the site investigator or staff designee (including third parties authorized by the site investigators) will access the UK reconsented participants' medical record (general practitioner's or hospital's record) to determine if the medical event meets with the definition of wheeze provided by the Sponsor (see Section 8.1.2.4). If so, the event and related complementary information (including any medications prescribed during wheeze) will be retrospectively collected.

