5.2. Handling of Dropouts, Missing Data, and Outliers

5.2.1. Handling of Missing Efficacy Data

Efficacy data (ie, LRTI hospitalization) will be collected through the participants' medical records and reported in the eCRF by the site personnel or designee. Efficacy data will be analyzed accounting for the follow-up time post-dosing/randomization up to the data cut-off date.

For the participants who do not have the efficacy endpoints of interest at the time of the Primary Analysis, the end date for the efficacy follow-up will be the end of the RSV season, or the last available date with confirmation of no such efficacy endpoints, or the cut-off date of the Primary Analysis, whichever occurs first. The efficacy follow-up will be censored at the end date.

For the participants who do not have the efficacy endpoints of interest through the RSV season at the time of the First Year Analysis, the end date for the efficacy follow-up will be the last available date with confirmation of no such efficacy endpoints or the end of RSV season whichever is earlier. The efficacy follow-up will be censored at the end date.

For the participants who do not have RSV LRTI hospitalization through Day 151/ Day 181 post-dosing/randomization, from 181 days post-dosing/randomization to 366 days post-dosing/randomization or from 366 days post-dosing/randomization to 731 days post-dosing/randomization, please refer to sections 6.6.4.3.2, 6.6.4.3.4, 6.6.4.3.5 and 6.6.4.3.6. For participants who do not have recurrent wheeze events through Day 366/ Day 731 post-dosing/randomization, please refer to section 6.6.4.3.7.

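### The Primary Analysis cut-off takes two dates by contact route, so person-time in the primary rate depends on how the family was reached; efficacy is biased only if routes or event capture differ by arm

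*SAP*

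**What the plan says.** SAP 6.6.1 defines the start of the season by country from surveillance. For the end it substitutes "the cut-off date (28Feb2023, except for site parent contact and medical call center contact, for which the date of database lock for Primary Analysis" applies. The sentence closes by saying that this date "will be used) will be used as end dates". For event-free infants still in the study, follow-up stops at the end of season, "the last available date with confirmation of no RSV LRTI hospitalization or the cut-off date whichever is earlier". A separate rule, "for the participants who had no contact for safety events at all throughout the efficacy follow-up period", sets the end date equal to the start date, which is one day of person-time.

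SAP 5.2.1 repeats the censoring rule with a single undated limit, "or the cut-off date of the Primary Analysis, whichever occurs first". SAP 6.7.8 likewise speaks of one cut-off.

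The contact routes are described in the protocol:
- Section 8.1, call centre: "each time a health event will be captured on the eDiary, a medical call center will contact parents/LARs".
- Section 7.3, site call: "If there is no answer after the e-reminders, the site and/or designee will call the parents or LARs".
- Section 8.1, families outside the eDiary: "Parents/LARs who don't have access to the eDiary will be requested to contact directly the investigation site".

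**The concern.** The end of season and the cut-off are the same two-valued date, and the only other limit is the last confirmation of no event. Nothing in 6.6.1 therefore holds a family reached by the site or call centre to 28 February, while a family known only through the eDiary cannot pass it. Which group an infant falls into is decided after randomization, in an open-label trial whose protocol (6.3.2) accepts that equal attention to the two groups cannot be ensured and that the direction of any bias is uncertain.

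The same follow-up rule feeds the primary test, the very severe endpoint (SAP 6.6.4.1), the country tests (6.6.4.2), and the Poisson and Cox analyses. The tipping-point analysis imputes only for discontinuation or a missing or undone RSV test, and the First Year re-run (6.6.7.10) keeps the same cut-off and rules. None of these would show the effect.

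**Working it through.** The plan gives no figure for this effect. Its nearest number is 61 events for at least 90% power at 60% efficacy. The exact conditional binomial test gives 92.2% power at 61 events, so that figure reproduces, and the sample size is not affected by this point.

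**Inputs**
- Cut-off 28 Feb 2023 (SAP 6.6.1). Planned enrolment 1 Sep 2022 to 28 Feb 2023, 181 days (Protocol 4.1).
- Mean time to cut-off under uniform accrual (assumed), with the SAP's inclusive day count: (0 + 180)/2 + 1 = 91 days.
- The lock date is not stated. Assumed range: 6 Apr 2023 (date of SAP version 3.0) to 30 Apr 2023 (latest date for the Primary Analysis), or 37 to 61 days after cut-off.
- Shares of infants with a late contact: not documented. Assumed 20% v 10% and 30% v 20%.

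**Formula.** The rate ratio is (CN/CC) × (NC/NN). With no added events, it is multiplied by (91 + g·pC)/(91 + g·pN). Here g is the mean time gained per late-contacted infant, and pC and pN are the late-contact shares in control and nirsevimab.

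**Literal reading.** Time stops at the last confirmation, so contacts spread evenly between cut-off and lock gain half the gap on average: g = 18.5 to 30.5 days. The full gap applies only if every late contact falls on lock day, which is the upper bound.

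| g (days) | pC v pN | Factor | True 60% reads | Shares reversed |
|---|---|---|---|---|
| 18.5 | 20% v 10% | 94.70/92.85 = 1.020 | 59.2% | 60.8% |
| 18.5 | 30% v 20% | 96.55/94.70 = 1.020 | 59.2% | 60.8% |
| 30.5 | 20% v 10% | 97.10/94.05 = 1.032 | 58.7% | 61.3% |
| 30.5 | 30% v 20% | 100.15/97.10 = 1.031 | 58.7% | 61.2% |
| 37 (bound) | 20% v 10% | 98.40/94.70 = 1.039 | 58.4% | 61.5% |
| 37 (bound) | 30% v 20% | 102.10/98.40 = 1.038 | 58.5% | 61.4% |
| 61 (bound) | 20% v 10% | 103.20/97.10 = 1.063 | 57.5% | 62.4% |
| 61 (bound) | 30% v 20% | 109.30/103.20 = 1.059 | 57.6% | 62.2% |

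Equal shares give a factor of 1 and no shift. If admissions after 28 February also entered through call-centre contacts, both arms' rates would rise. That cancels in the ratio when the extended share is the same in both arms.

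**Narrower reading.** Suppose late site and call-centre contacts only confirm status back to 28 February. Scheduled eDiary contacts are 30 days apart, so an eDiary-only infant stops on average about 15 days short, at 91 − 15 = 76 days. A late-contacted infant is credited with 91. With 20% v 10%, the factor is (76 + 15 × 0.2)/(76 + 15 × 0.1) = 79.0/77.5 = 1.019, so 60% reads 59.2%, or 60.8% reversed. An infant enrolled from 30 January has no scheduled eDiary contact by 28 February, because D31 falls in March. That is 30/181 = 17% of infants under uniform accrual. Without any other contact, each contributes one day.

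**The case against.** The strongest reply is that the exception is a data-retrieval limit: contact records made up to lock are used, but the efficacy window closes on 28 February. Much supports this. The exception names a type of contact rather than a class of infant. The season is otherwise defined by country, so an end date varying by family would be odd. SAP 6.7.8 explains the re-run by delay in data collection, which separates event date from collection date. The document history (versions 4.0 and 5.0) also refers to the cut-off without an exception. The undated cut-off in 5.2.1 and 6.7.8 fits this reading and does not conflict with 6.6.1.

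This stands as a plausible intention, but 6.6.1 does not say it, and the narrower reading leaves follow-up dependent on route.

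Other points also stand. The term for site contact is not defined, and the site may hear from families for reasons other than non-response. The call centre responds to any health event, not only admissions. Efficacy data are taken from medical records, so late events entering by contact route are a possibility, not a stated rule. The Day 151 and Day 181 analyses use windows fixed from Day 1 and avoid the two dates, but they are not confirmatory. Monthly eDiary responses and follow-up time are to be summarised (SAP 6.6.7.8), though not by contact route.

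A reader might infer that the primary efficacy estimate is biased, or that every late-contacted infant gains 37 to 61 days. The documents support neither: they report no arm difference in contact route, and the last-confirmation rule stops time before lock for most such infants.

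**Conclusion.** The concern holds as a defect in the stated rule: primary person-time depends on contact route under either reading of SAP 6.6.1. Bias in the rate ratio is conditional on late-contact shares or event capture differing by arm. The 10-point difference, lock date, accrual pattern, even spread of contacts and absence of added events are all assumptions. On them the shift is about 0.8 to 1.3 points either way, with 57.5% and 62.4% as outer bounds. For comparison, 17 v 44 events (61 in total) with equal person-time gives 61.4% efficacy (95% CI 31.0 to 79.3). A large effect would survive, so this is a correction worth making, not a threat to a clear result.

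**What to change.** In SAP 6.6.1, use one efficacy window for every infant: admissions and person-time up to 28 Feb 2023, whatever the contact route. State that contacts of every kind between 28 February and database lock, eDiary answers included, serve only to establish event status and event-free time up to 28 February. Apply the same rule to 6.6.4.1, 6.6.4.2 and the 6.6.7.10 re-run. SAP section 7 shows that the Primary Analysis has already been run, so present the result as a labelled sensitivity re-run, not a replacement. Add a table of last-confirmation date and contact route by arm, which would show whether the imbalance exists.

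The cost is SAP wording, one programming rule, one table and a re-run, with no new data collection. Some late person-days, and any admissions after 28 February, would be dropped.
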